5.6.3.3 Other safety endpoint(s)

Where appropriate, suicidality will be assessed by trained study personnel using the Columbia-Suicide Severity Rating Scale (C-SSRS; Columbia University Medical Center, 2008).

The “Already Enrolled” version of the C-SSRS should be completed at the Termination Visit or Early Termination Visit if the participant reaches 6 years of age by the time that visit is conducted. Participants who are ≥ 6 years of age who require additional treatment with LCM oral solution and are approved to continue will be administered the “Already Enrolled” version of the C-SSRS at the first visit (scheduled or unscheduled) which occurs upon reaching 6 years of age. The “Already Enrolled” C-SSRS version will continue to be administered at each subsequent visit (scheduled or unscheduled) up to and including the Termination or Early Termination Visit.

Participant data listings of the data for the C-SSRS will be provided. No summaries of these results are planned.

5.7 Other Analyses

Not applicable.

5.8 Subgroup analyses

No other subgroup analyses are planned.

5.9 Interim Analyses

Not applicable.

5.10 Data Monitoring Committee (DMC) or Other Review Board

Not applicable.

6 SUPPORTING DOCUMENTATION

6.1 Appendix 1 Non-key analysis specifications

6.1.1 Baseline characteristics and demographics

Demographics and baseline characteristics will be summarized descriptively for the SS. The summary comprises age (years) at entry into EP0151, age (years) at entry into first pediatric study, and age at entry into EP0151 categorized as (24 months - <12 years), racial group (American Indian/Alaskan Native, Asian, Black, Native Hawaiian or Other Pacific Islander, White, and Other/Mixed), ethnicity (Hispanic or Latino, and not Hispanic or Latino), weight (kg), height (cm) and BMI (kg/m^2). The number of participants and percentage for age groups, gender and countries will also be presented for the SS.

Demographic data will also be listed for the SS.

6.1.2 Protocol deviations

Important protocol deviations defined in the important protocol deviations document, and additionally identified at the DEMs, will be listed. In addition, the number and percentage of

participants with at least 1 important protocol deviation will be summarized overall and by category of important protocol deviation (as defined in Section 5.1.2.6) for the SS.

6.1.3 Medical history

The number and percentage of participants with a medical history condition (except epilepsy), including both resolved and ongoing conditions that were not reported in the parent studies, will be summarized overall and by MedDRA® primary SOC and PT for the SS.

Lifestyle and family medical history for PDILI participants will be listed if it occurred.

6.1.4 Concomitant diseases and conditions

The number and percentage of participants with concomitant diseases and conditions (medical history conditions noted as ongoing at study entry for the EP0151 study), except epilepsy, will be summarized by SOC and PT for the SS.

6.1.5 Concomitant medications

Concomitant AEDs taken at the start of the EP0151 Treatment Period are defined as AEDs taken concomitantly with LCM at the time of first dose of LCM in EP0151. Ongoing concomitant medications from EP0034 and SP848 will be followed up and reported in this study.

The number of concomitant AEDs taken at the start of the EP0151 Treatment Period will be summarized for the SS based on the following categorization: 0 AEDs, 1 AEDs, 2 AEDs, 3 AEDs, and >3 AEDs. The number and percentage of participants taking concomitant AEDs at the start of the EP0151 Treatment Period will be summarized, separately, by WHODD chemical subgroup (level 4) and medication name, for the SS. AEDs taken as rescue medication will be excluded from the summary.

Concomitant AEDs taken during the EP0151 Treatment Period are defined as AEDs taken concomitantly for at least one day in common with LCM in EP0151.

The number and percentage of participants taking concomitant AEDs during the EP0151 Treatment Period will be summarized overall and, separately, by WHODD chemical subgroup (level 4) and medication name, for the SS. AEDs taken as rescue medication will be excluded from the summary.

VNS is allowed and will not be counted as a concomitant AED.

The number and percentage of participants taking concomitant non-AEDs during the EP0151 Treatment Period will be summarized overall and, separately, by WHODD anatomical main group (level 1) and therapeutic subgroup (level 2), for the SS.

Potential hepato-toxic medications inquiries and physical examination for PDILI will be listed if it occurred.

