### Early Termination Visit with tapering of LCM

Study participants who discontinue prematurely from EP0151 and who will not continue further treatment with LCM should gradually taper LCM. These study participants will perform an Early Termination Visit followed by the visits required for the End of Study Period. Study participants should be tapered off LCM at the recommended decrements (Table 6-2). The Taper Period is up to 4 weeks; a slower taper or faster taper is permitted, if medically necessary; however, the maximum duration of tapering should not exceed 6 weeks. All study participants who taper off LCM will attend a Final Visit 30 days after the final dose of LCM. In the case of LCM withdrawal and taper, the Investigator is allowed to add any other antiepileptic drugs (AEDs) during the End of Study Period, following the Investigator's medical judgment.

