1.2 Study design

EP0151 is a multi-center, long-term, open-label, follow-up study to assess the long-term use of LCM oral solution (a formulation suitable for administration to children; also referred to as syrup) for pediatric study participants \leq 6 years of age with epilepsy who have completed either EP0034 or SP848.

Study participants who complete EP0034 or SP848 will be offered participation in EP0151 and will have access to open-label follow-up treatment with LCM. Approximately 80 to 100 study participants are estimated to be eligible for enrollment.

Visit 1 for EP0151 will be the same as Visit 13 in EP0034 or SP848. Clinic visits will be scheduled approximately every 26 weeks relative to the EP0151 Visit 1 date. A visit window of ± 7 days relative to Visit 1 is applicable for all regularly scheduled visits.

All study participants in EP0151 will receive LCM. The Investigator may maintain the study participant's LCM dose from previous studies EP0034 or SP848, decrease the dose in decrements of 2mg/kg/day per week to a minimum dose of LCM 2mg/kg/day, or increase the dose in increments of 2mg/kg/day per week up to a maximum dose of LCM 12mg/kg/day or 600mg/day, whichever is lower, administered twice per day (BID).

This study involves a Treatment Period of approximately up to 205 weeks, depending on the age of the study participant, and an End of Study Period of approximately 8 weeks (including a

Taper Period and a Safety Follow-Up Period). Study participants who reach the end of the study and choose to continue treatment with LCM may be immediately prescribed LCM. The Termination Visit at the end of the Treatment Period will be the last study visit completed for study participants who continue treatment with prescribed LCM. Study participants who choose not to continue with LCM treatment and who are taking a dose of 3mg/kg/day or higher will enter an End of Study Period following completion of the Termination Visit or Early Termination Visit, and will gradually taper from LCM treatment during the Taper Period; a Final Visit will be conducted 30 days after the final dose of LCM.

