5.1.2 General study level definitions

5.1.2.1 Analysis Time Points

5.1.2.1.1 First and last dose of LCM

Unless otherwise noted, all references to the first dose of LCM in this SAP refer to the first dose of LCM during EP0151 (ie, not the first dose of LCM from the previous study in which participants participated prior to EP0151). Unless otherwise noted, all references to the last dose of LCM in this SAP refer to the last dose of LCM in EP0151.

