5.1.2.1.3 Study periods

This study consists of a Treatment Period and an End of Study Period.

Treatment Period

This is defined as the period of time from the date of first dose of LCM (Visit 1) to the Termination Visit for participants who complete the study or to the ETV for those who discontinued.

End of Study Period (Taper Period + Safety Follow-up Period)

This is defined as the period of time from the day after the end date of the Treatment Period and extending through to the Final Visit or last contact with the subject. No scheduled visits are planned in the Taper Period. Final Visit is the only scheduled visit in Safety Follow-up Period.

The maximum total duration of the study will be approximately 213 weeks, including an approximate 205-week Treatment Period and up to an 8 week Post-Treatment Period (4-week Taper Period and a Final Visit 30 days after the last dose). The end of the study is defined as the date of the last visit of the last study participant in the study.

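### The SAP 6.1.5 table of concomitant AEDs in the EP0151 Treatment Period also counts AEDs first started in the taper, after that period has ended

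*SAP*

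**What the plan says.** SAP 6.1.5 (Concomitant medications) has two AED summaries. The first is fixed at the first EP0151 dose of LCM. The second carries the Treatment Period label and reports participants overall, by chemical subgroup and by drug name. Its members "are defined as AEDs taken concomitantly for at least one day in common with LCM in EP0151". The only AEDs left out are those given as rescue medication.

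The periods are set in SAP 5.1.2.1.3 and 5.1.2.1.4. The Treatment Period runs from first dose to the Termination Visit, or to the ETV for those who discontinue. Of the End of Study Period, which contains the taper, the SAP says: "This is defined as the period of time from the day after the end date of the Treatment Period".

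LCM does not stop at that boundary. Under SAP 1.2, children on 3mg/kg/day or more who do not continue LCM "will gradually taper from LCM treatment during the Taper Period; a Final Visit will be conducted 30 days after the final dose of LCM". SAP 5.1.2.1.1 adds that "all references to the last dose of LCM in this SAP refer to the last dose of LCM in EP0151", so taper doses are included.

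New AEDs are foreseen at this point. Protocol 4.1 states that, in LCM withdrawal and taper, "the Investigator is allowed to add any other antiepileptic drugs (AEDs) during the End of Study Period"; footnote e to protocol Table 1-1 says the same. The taper is normally up to 4 weeks, and "the maximum duration of tapering should not exceed 6 weeks".

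**The concern.** The label and the membership rule of one table use different time windows. The label points to a period that closes at the Termination Visit or ETV. The rule stays open until the last LCM dose, which for a tapering child comes later. A drug started because LCM was being withdrawn is then reported as taken during the Treatment Period, and nothing in the table separates it from drugs that were.

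The error runs in one direction: it adds AEDs and never removes them. It matters most for the row showing any concomitant AED. Protocol 6.5.1 allows other AEDs to be withdrawn to reach LCM monotherapy, and the complement of that row shows who took no other AED. A child on monotherapy up to the Termination Visit or ETV who starts another AED on the first taper day drops out of that group.

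**Working it through.** **Inputs**
- Treatment Period end date, T: Termination Visit or ETV (SAP 5.1.2.1.4).
- Last LCM dose in EP0151, L: end of taper for those who taper (SAP 1.2, 5.1.2.1.1).
- Taper length: 2, 3 or 4 weeks in protocol Table 6-2 (14, 21, 28 days); at most 6 weeks (42 days) in protocol 4.1.
- S: start date of an AED first started on or after first dose. I assume LCM is taken on each taper day and the AED is taken on its start day.

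**Step 1: where the plan puts the taper.** The stated maximum of about 213 weeks can be reproduced: 205 + (28 + 30)/7 = 205 + 8.29 = 213.29 weeks. The 28 taper days sit outside the 205-week Treatment Period.

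**Step 2: the two rules.**
- SAP 6.1.5 as written: counted if S ≤ L.
- Limited to the Treatment Period: counted if S ≤ min(L, T).
- They disagree exactly when T < S ≤ L.

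**Step 3: apply them**, with T at week 205 (205 × 7 = day 1435).

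| Taper | L | AED started on T+1, T+7 or L | AED started on L+1 |
|---|---|---|---|
| 14 days | T+14 | SAP: counted; limited: not counted | neither |
| 21 days | T+21 | SAP: counted; limited: not counted | neither |
| 28 days | T+28 | SAP: counted; limited: not counted | neither |
| 42 days | T+42 | SAP: counted; limited: not counted | neither |

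The misclassification window is the whole taper: normally up to 28 days, at most 42.

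**Step 4: who is affected.** Only children who taper and start a non-rescue AED in that window. The following are not affected:
- children who move straight to prescribed LCM and so have no study taper;
- AEDs already overlapping LCM before the taper;
- AEDs started on the Termination Visit or ETV date itself, because the End of Study Period begins the next day;
- AEDs started after the last LCM dose.

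The overall row changes only for a child with no other AED counted before the taper.

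**Step 5: size.** The documents give neither the share of children who taper nor the share who then start an AED. By assumption only, if 5% to 30% of the anticipated 80 to 100 participants did both, the range would be 80 × 0.05 = 4 to 100 × 0.30 = 30 children.

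**The case against.** The strongest reply is that overlap with LCM is the more useful definition. TEAEs are counted to 30 days after the final LCM dose (SAP 5.3.1), so taper events belong to a primary endpoint, and an AED taken alongside LCM in the taper is real co-medication for them. That stands, and it is why these drugs should stay visible in a table. It does not rescue the label: the rule stops admitting new AEDs at the last LCM dose, so it matches neither the Treatment Period nor the TEAE window. The SAP does apply the Treatment Period limit to modal and maximum dose (5.1.2.4).

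It is also fair to say that the table sits under non-key specifications in a study without hypothesis tests, and that listings show medication dates as reported, so most such AEDs can be traced. Both points limit the importance but leave the table's counts unchanged.

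Three stronger readings are tempting and not supported:
- **That the background regimen is misreported.** The SAP does not call this table background treatment, and the separate summary at first dose, which holds the count from 0 to more than 3 AEDs, is unaffected.
- **That children who stop LCM will look more heavily treated than those who continue.** No such comparison is planned. Summaries are overall and by age group (SAP 5.1), with no other subgroup analyses (SAP 5.8). Only the reported figures are inflated.
- **That non-AEDs have the same fault.** Their sentence in 6.1.5 names the Treatment Period and has no conflicting definition.

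**Conclusion.** The inconsistency is real and follows from the SAP's own definitions. As written, non-rescue AEDs started after the Treatment Period ends, up to and including the day of the last LCM dose, enter a table labelled with that period. The overall and by-drug counts can only go up, and the group with no concomitant AED can only shrink.

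The consequence is limited to one descriptive table; no primary endpoint value and no analysis set changes. The number of children cannot be derived. A reader might infer a large effect: assuming that 20% to 40% taper and 50% to 100% of those start another AED gives 80 × 0.2 × 0.5 = 8 to 100 × 0.4 × 1.0 = 40 children. The documents support neither that range nor the 4 to 30 above. The finding rests on the wording and needs no rate.

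**What to change.** In SAP 6.1.5, keep the overlap with LCM and add the period limit. For example: AEDs whose use overlaps LCM dosing by one day or more, where that day lies between the date of first EP0151 dose and the end date of the Treatment Period (Section 5.1.2.1.4), inclusive. Add a separate table of AEDs started after that date, labelled as started in the End of Study Period, so that co-medication during taper TEAEs stays visible.

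The overlap requirement should not be replaced by dates alone. Protocol Table 10-1 provides for study medication to be discontinued while the child stays in the study for follow-up. An AED started after such a stop but before the ETV shares no day with LCM, yet a date-only rule would count it.

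The minimum alternative is to relabel the existing table as AEDs taken during LCM exposure in EP0151.

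The cost is one sentence and one extra table, with no new data. One weakness remains. SAP 5.1.1.2 sets a missing start day to the first of the month (unless LCM began that month), so a partially dated AED from the month of the Termination Visit or ETV could still fall inside the Treatment Period. A footnote giving the number of imputed start dates would cover this.

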6.1.6 Other significant AEs

Table 6-1: Other significant AEs

MedDRA Preferred Term
CARDIAC AND ECG RELATED TERMS
Atrioventricular block third degree

MedDRA Preferred Term
Atrioventricular block second degree
Bradyarrhythmia
Bradycardia
Cardiac pacemaker insertion
Atrial fibrillation
Atrial flutter
Sinus bradycardia
Ventricular tachycardia
Ventricular fibrillation
Heart Rate decreased
Sick sinus syndrome
Atrial conduction time prolongation
Atrioventricular dissociation
Conduction disorder
Cardiac arrest
Cardiac fibrillation
Cardiac flutter
Sinus arrest
Torsade de pointes
Ventricular asystole
Ventricular flutter
Ventricular tachyarrhythmia
Implantable defibrillator insertion
SUICIDALITY RELATED TERMS
Completed suicide
Depression suicidal
Suicidal behaviour
Suicidal ideation
Suicide attempt
Intentional self-injury

MedDRA Preferred Term
Self injurious behaviour
Self-injurious ideation
Intentional overdose
Multiple drug overdose intentional
Poisoning deliberate
ADDITIONAL TERMS
Loss of consciousness
Syncope
Appetite disorder
Decreased appetite
Diet refusal
Hypophagia
Food aversion
Abnormal behaviour

6.1.7 AEs for PDILI

The following MedDRA PTs are defined as AEs for PDILI:

Table 6–2: AEs for PDILI

MedDRA Preferred Term for PDILI
Acute hepatic failure
Alanine aminotransferase increased
Allergic hepatitis
Aspartate aminotransferase increased
Asterixis
Blood bilirubin abnormal
Blood bilirubin increased
Cholestasis
Cholestatic liver injury
Cholestatic pruritus
Chronic hepatitis

MedDRA Preferred Term for PDILI

Coma hepatic
Cryptogenic cirrhosis
Drug-induced liver injury
Hepatic cirrhosis
Hepatic encephalopathy
Hepatic failure
Hepatic infiltration eosinophilic
Hepatic necrosis
Hepatic steatosis
Hepatitis
Hepatitis acute
Hepatitis cholestatic
Hepatitis chronic active
Hepatitis chronic persistent
Hepatitis fulminant
Hepatitis toxic
Hepatobiliary disease
Hepatocellular foamy cell syndrome
Hepatocellular injury
Hepatotoxicity
Hyperbilirubinaemia
Icterus index increased
Jaundice
Jaundice cholestatic
Jaundice hepatocellular
Liver disorder
Liver injury
Mixed liver injury
Non-alcoholic steatohepatitis
Ocular icterus
Subacute hepatic failure

This document cannot be used to support any marketing authorization
PUBLIC COPY

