### **8.2.3 Clinical safety laboratory assessments**

See Appendix 2 (Section [10.2](#)) for the list of clinical laboratory tests to be performed and to the Schedule of Activities for the timing and frequency. Starting from Visit 2, blood specimens for routine assay of hematology and clinical chemistry testing will be analyzed by the local laboratory affiliated with the site. The individual laboratory parameter result data will not be collected in the eCRF; however, the Investigator will report any out of range results judged to be clinically significant as an AE.

The Investigator must review the laboratory reports, document this review, and record any clinically relevant changes occurring during the study in the AE section of the eCRF. The laboratory reports must be filed with the source documents. Clinically significant abnormal laboratory findings are those which are not associated with the underlying disease, unless judged by the Investigator to be more severe than expected for the participant's condition.

All laboratory tests with values considered clinically significantly abnormal during participation in the study or within 30 days after the last dose of study medication should be repeated until the values return to normal or baseline or are no longer considered clinically significant by the Investigator or Medical Monitor.

If such values do not return to normal/baseline within a period of time judged reasonable by the Investigator, the etiology should be identified and the Sponsor notified.

All protocol-required laboratory assessments, as defined in Appendix 2 (Section 10.2), must be conducted in accordance with the laboratory manual and the Schedule of Activities (Table 1-1).

If laboratory values from non-protocol specified laboratory assessments performed at the institution's local laboratory require a change in participant management or are considered clinically significant by the Investigator (eg, SAE or AE or dose modification), then the results must be recorded in the eCRF.

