**Table 10-1: Phase 3-4 liver chemistry stopping criteria and follow-up assessments**

Liver Chemistry Stopping Criteria	
ALT-absolute	ALT≥8xULN
ALT increase	ALT≥5xULN but <8xULN persists for ≥2 weeks ALT≥3xULN but <5xULN persists for ≥4 weeks
Bilirubina,b	ALT≥3xULN and bilirubin ≥2xULN (>35% direct bilirubin)
INRb	ALT≥3xULN and INR>1.5, if INR measured
Cannot monitor	ALT≥5xULN but <8xULN and cannot be monitored weekly for ≥2 weeks ALT≥3xULN but <5xULN and cannot be monitored weekly for ≥4 weeks
Symptomatic	ALT≥3xULN associated with symptoms (new or worsening) believed to be related to liver injury or hypersensitivity
Suggested Actions and Follow up Assessments	
Actions	

• Immediately discontinue study medication

• Report the event to UCB within 24 hours

• Complete the Liver Event eCRF, and complete an SAE data collection tool if the event also met the criteria for an SAEb

	
Follow-up Assessments	

• Viral hepatitis serologyd

• Obtain INR and recheck with each liver chemistry assessment until the transaminases values show downward trend

	

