5.6.2 Adverse Events

AEs will be tabulated by MedDRA system organ class (SOC) and MedDRA preferred term (PT). The number and percentage of participants experiencing each event at least once will be summarized. All summaries will be sorted alphabetically by SOC and by frequency of events within PTs, starting with the most frequent event overall.

AEs will be classified as ongoing at entry, treatment-emergent and post-treatment. Ongoing AEs at entry are defined as AEs which had an onset date prior to the first EP0151 dose of LCM.

TEAEs will be defined as those events which started on or after the date of first dose of LCM in EP0151, or events for which severity worsened on or after the date of first dose of LCM in EP0151. AEs which occur within 30 days after final dose of LCM in EP0151 will be considered treatment-emergent. Post-treatment AEs are defined as AEs which had an onset date after 30 days after the last dose of LCM.

All AEs reported during the study including ongoing AE at entry and post-treatment AEs will be provided in a participant data listing. Ongoing AEs from EP0034 and SP848 will be followed up and reported in this study.

An overview of the incidence of TEAEs will provide the overall summary of TEAEs and the numbers and percentages of participants with at least 1 TEAE, with a serious TEAE, with a drug-related TEAE, with a severe TEAE. The number and percentage of participant discontinuations due to TEAEs, the number and percentage of all deaths (if applicable), and the number and percentage of participants with TEAEs leading to death (if applicable) will also be summarized.

The number and percentage of participants who discontinued due to SAE (regardless of treatment emergent) will also be summarized.

The following summaries of AEs will be provided by MedDRA primary SOC and PT:

- Incidence of TEAEs
- Incidence of serious TEAEs
- Incidence of non-serious TEAEs
- Incidence of ongoing AEs at EP0151 study entry
- Incidence of TEAEs leading to discontinuation
- Incidence of SAEs leading to discontinuation
- Incidence of TEAEs related to potential drug-induced liver injury (PDILI) (defined in

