5.6.3 Additional Safety Assessments

5.6.3.1 Clinical laboratory evaluations

Starting from Visit 2, blood specimens for routine assay of hematology and clinical chemistry testing will be analyzed by the local laboratory affiliated with the site. The individual laboratory parameter result data will not be collected in the eCRF; however, the Investigator will report any out of range results judged to be clinically significant as an AE.

No laboratory data will be summarized in tables. Laboratory test for PDILI will be listed if it occurred. Blood sample collection for pharmacokinetics for PDILI and suspected hepatic event for PDILI will be listed if it occurred.

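### The PDILI incidence table rests on a closed list of preferred terms with no link to the Liver Event eCRF or Hy's Law reports, so it can undercount protocol-defined liver cases

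*SAP*

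**What the plan says.** SAP 5.6.2 names among its SOC and PT summaries the "Incidence of TEAEs related to potential drug-induced liver injury (PDILI) (defined in" Appendix 6.1.7). The same section repeats this summary with site and participant numbers. SAP 6.1.7 supplies the definition: "The following MedDRA PTs are defined as AEs for PDILI", followed by Table 6-2. The list includes "Alanine aminotransferase increased", its AST counterpart, "Blood bilirubin increased" and broad diagnoses such as "Drug-induced liver injury".

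Routine laboratory values offer no second route to a summary. Protocol 8.2.3 says "The individual laboratory parameter result data will not be collected in the eCRF"; out-of-range results judged clinically significant are reported as adverse events. SAP 5.6.3.1 adds "No laboratory data will be summarized in tables".

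The protocol has two case identifiers that do not depend on how an event is coded. For a participant who meets a liver stopping criterion, Table 10-1 tells the site to "Complete the Liver Event eCRF". Protocol 8.3.5 makes potential Hy's Law an adverse event of special interest, reportable within 24 hours.

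**The concern.** The protocol identifies a liver case by biomarkers and symptoms. The SAP's PDILI table identifies it by the code given to the reported wording. The two agree only when at least one of the child's events is coded to a Table 6-2 term, and the SAP provides no check that this happened.

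TEAEs are a primary endpoint, and a reader will take a PDILI table that shows zero to mean that no liver cases occurred. Under the stated rule, zero means only that no listed term was used. The table and the PDILI listings could also disagree in the study report, and no text says which prevails.

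**Working it through.** The plan has no sample-size, power or liver-rate figure to reproduce. The check is a search of the list, a trace of the other liver provisions, and simple arithmetic.

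**1. What the list contains.** Table 6-2 has 42 PTs.
- *aminotransferase*: 2 matches (ALT increased, AST increased).
- *bilirubin*: 3 matches (blood bilirubin abnormal, blood bilirubin increased, hyperbilirubinaemia). Icterus index increased is also listed.
- *transaminases*, *enzyme*, *function*, *gamma*, *phosphatase*: 0 matches.
- *INR*, *prothrombin*, *coag*, *conjugated*, *direct*: 0 matches.
- Broad diagnoses present: liver disorder, liver injury, hepatotoxicity, hepatobiliary disease, drug-induced liver injury.

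SAP 6.1.7 has no clause that admits other terms. SAP 5.6.2, by contrast, finds the growth, neurodevelopment, behaviour and endocrine TEAEs by manual medical review of the reported PTs.

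**2. Which liver sources feed which outputs.**

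| Source | What triggers it | Feeds the PDILI incidence table? |
|---|---|---|
| Table 6-2 PTs (SAP 6.1.7) | coded AE term | yes |
| Liver Event eCRF (protocol Table 10-1) | liver stopping criterion met | not stated |
| Potential Hy's Law report (protocol 8.3.5) | biomarker criteria | not stated |
| PDILI listings (SAP 5.6.1, 5.6.3.1, 5.6.3.2.2, 6.1.3, 6.1.5) | PDILI having occurred, undefined | no, listings only |
| All TEAEs by SOC and PT, and AE listing (SAP 5.6.2) | any reported TEAE | no, separate outputs |

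The SAP's other grouped-term table, Table 6-1, covers cardiac, suicidality and additional terms and has no hepatic term. The PDILI table is therefore the only summary table specific to the liver.

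**3. Trace of one case.** Suppose a child meets an ALT criterion in Table 10-1, stops study medication and has a Liver Event form. The site records the ALT and AST rise as one event in general wording, and it is coded to a term outside Table 6-2.
- PDILI incidence table: not counted.
- Its repeat with participant numbers: not shown.
- Overall TEAE tables and AE listing: shown.
- PDILI listings: cannot be determined. If *PDILI occurred* means a Table 6-2 term, the child is absent; if it means an eCRF record, the child is present and the listing contradicts the table.

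**4. INR and direct bilirubin.** Table 10-1 pairs INR>1.5 with ALT≥3xULN, and >35% direct bilirubin with both ALT≥3xULN and bilirubin≥2xULN. Every such case therefore has an ALT rise, for which a listed term exists. INR is outside the routine panel in protocol Appendix 2.

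**5. Size.** One omitted child changes the row by 100 × 1/N percentage points.
- N=80: 100 × 1/80 = 1.25 points.
- N=100: 100 × 1/100 = 1.0 point.

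Exact (Clopper-Pearson) 95% intervals for what the table would show:
- 0/80: 0 to 4.51%; 1/80: 0.03 to 6.77%.
- 0/100: 0 to 3.62%; 1/100: 0.03 to 5.45%.

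For zero events the upper limit is 1 − 0.025^(1/N), which gives 4.51% and 3.62%. SAP 5.1 also splits summaries by age group. There the change is 100 divided by the group size, hence larger, but the documents give no group sizes.

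**The case against.** The strongest reply is that the table is not the only place where a liver case can be seen. Three parts of it stand.

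- **Listings and reporting.** A reader might infer that the SAP finds liver cases only through Table 6-2. The documents do not support that. SAP 5.6.3.1 lists laboratory tests and suspected hepatic events for PDILI, and other sections list related data. The Liver Event form and Hy's Law reporting do not depend on coding.
- **Other tables.** A reader might infer that a real liver signal would disappear. It would not. Every TEAE stays in the overall tables and the listing. Protocol Appendix 2 requires possible Hy's Law cases to be reported as SAEs, so a treatment-emergent one would also enter the serious TEAE table.
- **INR and direct bilirubin.** A reader might see the missing INR and direct-bilirubin terms as serious gaps. Because both criteria also need ALT≥3xULN, they add little, and a stand-alone INR term would admit cases outside the protocol's criteria.

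It can also be said that protocol Appendix 3 asks for a diagnosis rather than signs, which favours the broad listed terms. Protocol 2.2.1 reports no clinically relevant laboratory changes in preliminary pediatric data, so cases may be few. Both points lower the likely number omitted. Neither links the table to the protocol's own case records or defines when the listings are triggered.

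**Conclusion.** The point holds as a conditional undercount in one descriptive table. Under the SAP's stated rule, a child who meets the protocol's liver criteria is left out of the only liver-specific summary table if none of the child's events is coded to the 42 terms. The SAP does not say how that table is reconciled with the PDILI listings.

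Each omission is worth 1.0 to 1.25 percentage points at the planned 80 to 100 participants, and in a small study it may decide whether the row reads 0 or 1. No hypothesis test is affected.

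The number of omissions is unknown. The documents give neither a liver-event rate nor the frequency of general enzyme wording, and they cannot show which general terms exist in the coding version named in SAP 5.1.2.9 (MedDRA v16.1). The missing link to the Liver Event form and the Hy's Law reports rests on none of these unknowns. This is a cheap improvement to make before database lock, not a threat to the study's conclusions.

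**What to change.** In SAP 6.1.7 and 5.6.2, count a participant as a PDILI case if any of these holds:

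1. a Table 6-2 PT, or another reported PT judged liver-related at medical review before database lock, including general liver-enzyme or transaminase terms if reported;
2. a completed Liver Event eCRF or a suspected hepatic event record;
3. a potential Hy's Law report under protocol 8.3.5.

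The any-of rule is useful because Table 10-1 places completion of the form under a heading of suggested actions, so a form may not exist for every case.

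Add a top row, *participants with any PDILI event*, that shows the source of each count, and keep the SOC and PT rows beneath it. Footnote that a participant identified only by a form or report appears in the top row alone. Apply the SAP's existing treatment-emergent window to the date of the form or report. Use the same definition for the repeat with participant numbers and as the trigger for every PDILI listing, so that tables and listings agree.

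The cost is SAP wording, a short medical review of reported PTs, and a little programming from records the protocol already calls for. The count may include a few non-specific cases; the source column lets a reader see them.
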